9.1.7 Vital Signs

Resting (preferably a minimum of 5 minutes) measurements of body temperature, blood pressure, pulse and respirations will be performed and recorded as noted in the Schedule of Events.

9.1.8 Oximetry

A resting (preferably a minimum of 5 minutes) measurement of oximetry will be measured on room air and recorded at as noted in the Schedule of Events.

9.1.9 Participant Questionnaire: Quality of Life for Children with Epilepsy Parent Form (QOLCE)

The QOLCE is a parental questionnaire used to probe the quality of life of children with epilepsy. It is a 4-page survey where parents are asked to rate their child and takes less than 10 minutes to complete. The questionnaire will be given at the end of the 1-month baseline period, at the end of the 3-week dosing period, and again at the end of the 3-month follow-up period.

9.1.10 Participant Questionnaire: Nisonger Child Behavioral Rating Form (NCBRF)

The NCBRF is a 66-item parental questionnaire regarding their child's behavior. It should take about 5-10 minutes to complete. The questionnaire will be given at the end of the 1-month baseline phase, at the end of the 3-week treatment phase, and again at the end of the 3-month follow-up period.

9.1.11 Epilepsy Diary

Participants and their parents/guardians will be requested to complete a daily diary to record any new symptoms in between visits, and most importantly to record seizures. This diary will be mandatory during enrollment in the study. The diary will include the numbers and types of seizure events that occur daily and will be requested to be completed daily to avoid memory bias. The diary will be reviewed as noted in the Schedule of Events and adverse events will be recorded in the case report form (CRF), as applicable.

9.1.12 Investigator Opinion

As specified in evaluations by visit, at the start of the visit the investigator will opine on the status of the seizures recorded – whether they seem to be the same, worse, somewhat better, or better when compared to the prior visit. This will be labeled and treated as an opinion, and will be based on the recorded seizure frequencies, the descriptions of the seizures as provided by participants and their families, and expert experience.

9.1.13 Columbia-Suicide Severity Rating Scale (C-SSRS)

The C-SSRS is a suicidal ideation and behavior rating scale to identify risk in participants. The questionnaire will be given at the end of the 1-month baseline phase, at the end of the 3-week treatment phase, and again at the end of the 3-month follow-up period. Participant serious suicidal ideation scores must remain below a 4 in order to stay on study.

9.1.14 Adverse Events

Information regarding occurrence of adverse events will be captured throughout each participant's study participation, starting at enrollment and ending once the participant has terminated from the study. Duration (start and end dates), grade, seriousness, outcome, treatment and relation to study drug will be recorded on the CRF.

9.2 Clinical Laboratory Measurements

9.2.1 Hematology

Blood will be obtained as noted in the Schedule of Events and sent to each site's clinical hematology lab for a complete blood count (hemoglobin, hematocrit, red blood cell count, white blood cell count, white blood cell differential, and platelet count). If values are found to be abnormal, a sample will be collected and these parameters re-evaluated at the next study visit. If blood sample is unusable for testing, a second sample will be requested from the patient provided blood volume total is within safety range.

9.2.2 Blood Chemistry Profile

Blood will be obtained as noted in the Schedule of Events and sent to each site's clinical chemistry lab for determination of sodium, potassium, chloride, bicarbonate, calcium, fasting glucose, albumin, total protein, BUN, serum creatinine, total bilirubin, AST, ALT, alkaline phosphatase, uric acid, phosphorus, fasting serum lipid profile (total cholesterol, triglycerides, HDL and LDL). If values are abnormal, a sample will be collected and these parameters re-evaluated at the next study visit. If blood sample is unusable for testing, a second sample will be requested from the patient provided blood volume total is within safety range.

9.2.3 Pregnancy Test

Urine or blood (approximately 2 cc) will be collected from females who are of childbearing age and capable of becoming pregnant for a pregnancy test as noted in the Schedule of Events and tested in clinic according to site standard procedures. If urine test is positive, confirmation with appropriate blood testing is to be performed.

9.3 Pharmacokinetic Measurements

No pharmacokinetic measurements will be attained for this study.

9.4 Research Laboratory Measurements

Whole blood rapamycin trough levels will be drawn for three consecutive weeks. If blood sample is unusable for testing, a second sample will be requested from the patient provided blood volume total is within safety range.

9.5 Specimens for Long-Term Biorepository Storage

No additional specimens designated for this study will be kept for long-term bio-repository storage.

10 EVALUATIONS BY VISIT

10.1 Screening Assessments (Day -14 to 0)

1. Review the study with the participant (participant's legal representative) and obtain written informed consent and HIPAA authorization and assent, if appropriate.
2. Review eligibility (including epilepsy history)
3. Perform extended physical examination
4. Record demographics data
5. Record medical history, including a history of epilepsy, diagnosis date, and prior epilepsy treatments.
6. Vital signs (Height, pulse, blood pressure, respiration rate, temperature and weight)
7. Current medications and baseline conditions
8. Neurologic exam
9. Pulse oximetry (must be >93)
10. Laboratory assessments as required per the schedule of evaluations (need to be from within the last 30 days)
 - a. Complete Blood Count (CBC) with differential and platelet count
 - b. Blood chemistry assessment, including:
 - i. Sodium, potassium, chloride, bicarbonate, calcium, fasting glucose, albumin
 - ii. Total protein, BUN, serum creatinine
 - iii. Total bilirubin, AST, ALT, alkaline phosphatase, uric acid, phosphorus
 - iv. Fasting serum lipid profile (total cholesterol, triglycerides, HDL and LDL)
 - c. Coagulation assessment, including prothrombin time, partial thromboplastin time, international normalized ratio (PT/PTT/INR)

- d. Hepatitis B and C screening. Hepatitis B screening can be deferred in participants who have a history of having received the entire Hepatitis B immunization series and documentation is provided.
- e. Serum or urine pregnancy test: If participant is of child-bearing potential, pregnancy test should be done at screening and monthly thereafter. If urine test is positive, confirmatory blood testing will be performed.
- f. HIV seropositivity screening, if necessary.

11. If available and consent to archive has been given: Archival brain tissue tumor samples from a prior surgery will be used to test for molecular analyses. An email from the pathology/genetics department(s) may be used to confirm tissue availability at the time of enrollment.

10.2 Visit 1 – may also be Screening visit (Day 0)

1. Review the study with the participant/participant's legal representative and obtain written informed consent and HIPAA authorization and assent, if appropriate.
2. Assign the participant a unique screening number.
3. Record concomitant medications.
4. Perform abbreviated physical exam
5. Measure and record height and weight.
6. Obtain and record vital signs.
7. Initiate epilepsy diary

10.3 Visit 2 – End of Baseline (Day 30 +5/-2 days)

1. Review participant diary for compliance and seizure frequency.
2. Ensure participant has had >8 seizures in the last 30 days without 2 weeks of seizure freedom to continue onto next phase.
3. Collect baseline AEs
4. Administer C-SSRS, QOLCE and NCBRF
5. Record changes to concomitant medications.
6. Perform abbreviated physical exam
7. Obtain and record vital signs. Pulse oximetry must be >93 to continue.
8. Collect blood for clinical laboratory tests (chemistry, hematology).
9. Collect urine for pregnancy test (if child-bearing potential).
 - a. If positive confirm with blood test
10. Laboratory assessments as required per the schedule of evaluations
 - a. Complete Blood Count (CBC) with differential and platelet count.
 - b. Blood chemistry assessment, including:

- i. Sodium, potassium, chloride, bicarbonate, calcium, fasting glucose, albumin,
- ii. Total protein, BUN, serum creatinine.
- iii. Total bilirubin, AST, ALT, alkaline phosphatase, uric acid, phosphorus,
- iv. Fasting serum lipid profile (total cholesterol, triglycerides, HDL and LDL)

11. Coagulation assessment, including prothrombin time, partial thromboplastin time, international normalized ratio (PT/PTT/INR).

10.4 Visits 3, 4, & 5: ABI-009 Doses 1-3 (+/-2 days)

1. Review adverse events.
2. Review epilepsy diary.
3. Investigator opinion regarding seizures recorded: same, worse, somewhat better, better.
4. Record changes to concomitant medications.
5. Perform abbreviated physical exam
6. Measure and record height and weight.
 - a. BSA calculation (Calculated ONLY on Dose 1 visit; to be recalculated only if the weight changes by > 10% in subsequent cycles)
7. Obtain and record vital signs. Pulse oximetry must be >93 to continue.
8. Collect blood for clinical laboratory tests (chemistry, hematology).
9. Laboratory assessments as required per the schedule of evaluations
 - a. Complete Blood Count (CBC) with differential and platelet count
 - b. Blood chemistry assessment (required for Visit 4), including:
 - i. Sodium, potassium, chloride, bicarbonate, calcium, fasting glucose, albumin,
 - ii. Total protein, BUN, serum creatinine.
 - iii. Total bilirubin, AST, ALT, alkaline phosphatase, uric acid, phosphorus,
 - iv. Fasting serum lipid profile (total cholesterol, triglycerides, HDL and LDL)
10. Coagulation assessment, including prothrombin time, partial thromboplastin time, international normalized ratio (PT/PTT/INR)
11. Whole blood rapamycin trough levels
12. Dose modification as appropriate (only in the case of toxicities mandating a dose change as per section 8.6)
13. Administer study drug

10.5 Visit 6: Post-Dosing One-Week Assessment (+/-2 days)

1. Review adverse events.
2. Review epilepsy diary.

3. Investigator opinion regarding seizures recorded: same, worse, somewhat better, better.
4. Record changes to concomitant medications.
5. Perform abbreviated physical examination.
6. Obtain and record vital signs.
7. Collect urine for pregnancy test (if child-bearing potential).
 - a. If positive confirm with blood test
8. Collect blood for clinical laboratory tests (chemistry, hematology).
9. Laboratory assessments as required per the schedule of evaluations
 - c. Complete Blood Count (CBC) with differential and platelet count
 - d. Blood chemistry assessment, including:
 - i. Sodium, potassium, chloride, bicarbonate, calcium, fasting glucose, albumin,
 - ii. Total protein, BUN, serum creatinine.
 - iii. Total bilirubin, AST, ALT, alkaline phosphatase, uric acid, phosphorus,
 - iv. Fasting serum lipid profile (total cholesterol, triglycerides, HDL and LDL)
10. Coagulation assessment, including prothrombin time, partial thromboplastin time, international normalized ratio (PT/PTT/INR)
11. Whole blood rapamycin trough level
12. Administer C-SSRS, QOLCE, and NCBRF

10.6 Follow-up Visits 7, 8, & 9: 30, 60, and 90 Days Post-Dosing (+/-7 days)

1. Review participant diary for compliance and seizure frequency.
2. Safety follow-up labs at Visit 7 per PI discretion following Visit 6 labs.
3. Investigator opinion regarding seizures recorded: same, worse, somewhat better, better
4. Record changes to concomitant medications.
5. Perform abbreviated physical exam (30 days post-doing only).
6. Measure and record height and weight (at final study visit).
7. Obtain and record vital signs (30 days post-dosing only).
8. On final visit (90 days post-dosing) administer C-SSRS, QOLCE and NCBRF

10.7 Early Permanent Discontinuation of Study Dosing

1. Administer C-SSRS, QOLCE, and NCBRF.
2. Record any adverse events.
3. Record changes to concomitant medications.
4. Perform abbreviated physical exam.

5. Measure and record height and weight.
6. Obtain and record vital signs.
7. Collect blood for clinical laboratory tests (chemistry, hematology).
8. Collect urine for pregnancy test (if child-bearing potential).

11 ADVERSE EXPERIENCE REPORTING AND DOCUMENTATION

11.1 Adverse Events

An AE is any untoward medical occurrence in a clinical investigation of a participant administered a pharmaceutical product and that does not necessarily have a causal relationship with the treatment. An AE is therefore any unfavorable and unintended sign (including an abnormal laboratory finding), symptom or disease temporally associated with the administration of an investigational product, whether or not related to that investigational product. An unexpected AE is one of a type not identified in nature, severity, or frequency in the current Investigator's Brochure or of greater severity or frequency than expected based on the information in the Investigator's Brochure.

The Investigator will probe, via discussion with the participant, for the occurrence of AEs during each participant visit and record the information in the site's source documents. All AEs are to be collected, from enrollment through end of the subject's study participation, and recorded in the participant CRF. Attribution will be unrelated, unlikely, possible, probably, or definite.

Taking into account the targeted population and the secondary endpoints of the study, Grade 1 and 2 seizures as defined by the National Cancer Institute's Common Terminology Criteria for Adverse Events (CTCAE) v5 will not be tracked as adverse events and will not be included in the baseline patient assessment.

AE Severity

The CTCAE v5 should be used to assess and grade AE severity, including laboratory abnormalities. If the experience is not covered in the modified criteria, the guidelines shown in Table 3 below should be used to grade severity. It should be pointed out that the term "severe" is a measure of intensity and that a severe AE is not necessarily serious.

Table 7. AE Severity Grading

Severity (Toxicity Grade)	Description
Mild (1)	Mild; asymptomatic or mild symptoms; clinical or diagnostic observations only; intervention not indicated
Moderate (2)	Moderate; minimal, local or noninvasive intervention indicated; limiting age-appropriate Instrumental activities of daily living (e.g., preparing meals, using the telephone, managing money)
Severe (3)	Severe or medically significant but not immediately life-threatening; hospitalization or prolongation of hospitalization indicated; disabling; limiting self-care activities of daily living (e.g., bathing, dressing, feeding self, using toilet, taking medications)

Life-threatening (4)	Life-threatening consequences; urgent intervention indicated
Death (5)	Death related to AE

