5 CRITERIA FOR EVALUATION

5.1 Primary Endpoints

I. Safety

- DLT and MTD
- Incidence of adverse events and clinically significant abnormal lab values during dosing

II. Tolerability

- Voluntary or medically-determined withdrawal from study
- Adherence to medication regimen
- C-SSRS serious suicidal ideation score stays below a 4 rating

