5.2 Secondary Endpoints

I. Efficacy

- Seizure frequency
- Percentage reduction in seizure frequency
- Median percentage reduction in seizure frequency
- Response rate
- Frequency of seizure-free days
- Seizure-free rate
- Rapamycin blood level–response relationship

II. Quality of life and behavioral changes

- Quality of Life for Children with Epilepsy Parent Form (QOLCE) [1] and

- Nisonger Child Behavioral Rating Form (NCBRF) [2,3]
- Both will be completed at baseline, at the completion of maintenance, and at the completion of the 3-month follow-up period.

III. Weekly whole blood rapamycin trough levels for three consecutive weeks.

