8.5 Dose-Limiting Toxicities

Definition of Dose Limiting Toxicity (DLT):

Any grade 3 or higher toxicity and designated by the principle investigator as definitely or probably related (level of attribution) to the study drug, and occurring within 30 days of study drug dosing, or as specified per toxicity in the protocol.

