14 DATA SAFETY MONITORING

An independent Data Safety Monitoring Board consisting of at least three members will convene as frequently as necessary to review all participants enrolled on study. The DSMB will convene at minimum before the opening of each dose escalation cohort, and before opening MTD cohort expansion. All AEs experienced by participants on study will be summarized for review by the DSMB regardless of suspected relationship to the study drug. SAEs which are determined to be possibly, probably or definitely related to study drug will be reported to the DSMB within 5 days of occurrence, and any death of a participant that occurs while they are actively on study, regardless of relatedness to study drug, will be reviewed by the DSMB prior to enrollment of subsequent participants on study.

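### A rise confined to Grade 1-2 seizures counts as neither an adverse event nor a DLT, and the DSMB is not stated to receive seizure-frequency data before escalation or MTD expansion.

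*Combined protocol and SAP*

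**What the plan says.** - **AE exemption (Section 11.1).** With the target population and the secondary endpoints given as the reason, CTCAE v5 Grade 1 and 2 seizures "will not be tracked as adverse events and will not be included in the baseline patient assessment". Nothing is said about an increase over the participant's own baseline. Grade 3 and above are not exempted.
- **Primary endpoints (Section 5.1).** Safety is DLT and MTD plus "Incidence of adverse events and clinically significant abnormal lab values during dosing". Tolerability includes "Voluntary or medically-determined withdrawal from study".
- **DLT (Section 8.5).** "Any grade 3 or higher toxicity and designated by the principle investigator as definitely or probably related" to study drug, within 30 days of dosing or as specified per toxicity.
- **DSMB (Section 14).** The board meets at least before each escalation cohort and before MTD expansion. "All AEs experienced by participants on study will be summarized for review by the DSMB". Related SAEs and deaths are also named; diary data are not.
- **Investigator Opinion (Section 9.1.12).** The investigator judges the recorded seizures, "whether they seem to be the same, worse, somewhat better, or better when compared to the prior visit". It is not an endpoint in Section 5.
- **Efficacy (Sections 5.2 and 15.5).** The list includes seizure frequency itself, "Percentage reduction in seizure frequency", its median, the response rate (at least a 25% reduction), seizure-free days and seizure-free rate. No category is defined for worsening.

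**The concern.** Not logging each habitual seizure as an AE is sensible in participants who must have more than 8 seizures in 30 days to be dosed. The difficulty is that the exemption is written by grade alone, so it also covers a change in how often those seizures occur. More frequent seizures are an obvious harm to look for when a drug is added to a fixed antiepileptic regimen. The protocol's own background gives a reason to look after dosing as well: Section 1.6 describes animals whose seizures fell during rapamycin treatment and gradually increased after withdrawal, and this trial gives three weekly doses, stops, and observes for three months.

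At stake are the escalation decisions, taken on cohorts of three to six, and the final safety conclusion. Both rest on AEs and DLTs, and neither need reflect a rise that stays within Grade 1-2.

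**Working it through.** The plan states no figure for seizure worsening, so there is none to reproduce. The check traces one kind of event through the definitions, then looks at what the efficacy summaries would show.

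**1. Tracing a rise made up only of Grade 1-2 seizures**

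| Place | Does the rise appear? |
|---|---|
| AE incidence (11.1, 5.1, 15.3) | No: these grades are not tracked |
| DLT count (8.5) | No: Grade 3 or higher is required |
| DSMB inputs named in Section 14 | No: AEs, related SAEs, deaths |
| Hospitalization (15.3), withdrawal (5.1) | Only if the rise leads to one |
| Daily diary (9.1.11, 16.1) | Yes |
| Investigator Opinion (9.1.12) | At the visit where it is first seen |
| Secondary efficacy (15.5) | Yes, with no worsening category |

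**2. What the escalation rule cannot see.** In the 3+3 design, if an event with per-participant probability p counted, a level would pass with probability (1−p)³ + 3p(1−p)²·(1−p)³. The documents give no p, so these values are assumptions:

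| p | 0.1 | 0.2 | 0.3 | 0.4 | 0.5 |
|---|---|---|---|---|---|
| Pass probability if the event counted | 0.91 | 0.71 | 0.49 | 0.31 | 0.17 |
| Pass probability on this event as written | 1.00 | 1.00 | 1.00 | 1.00 | 1.00 |

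This shows the rule's blind spot. It does not propose a DLT definition.

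**3. What the efficacy summaries show.** The Section 15.5 formula, (baseline − follow-up)/baseline, is signed:
- 3 to 1.5 per week: +50%
- 3 to 3 per week: 0%
- 3 to 6 per week: (3 − 6)/3 = −100%
- 10 to 30 per month: (10 − 30)/10 = −200%

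Individual values therefore reveal a rise. The median and response rate can hide one. Take nine invented participants, five at +30% and four at −100% (doubled):
- median reduction = +30%
- response rate = 5/9 = 56%
- mean = (5 × 30 − 4 × 100)/9 = −28%

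The four whose seizures doubled are counted exactly as four with no change would be.

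**4. What the Investigator Opinion shows.** Dose 1 is Visit 3 and the opinion is given at the start of a visit. A lasting step-up after Dose 1 is therefore *worse* at Visit 4. Compared with the prior visit, it is then *same* at Visits 5 to 9: five visits under Sections 10.4 to 10.6, or four under Appendix 1, which marks no opinion at Visit 9.

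**5. Whether worsening could simply be logged as an AE at each visit.** Suppose the trigger were a count at least 25% above baseline since the last visit. Assume Poisson counts, no drug effect and a baseline rate known exactly. The chance of a false flag is:

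| Seizures per 30 days | Expected per week | Flagged at | Per weekly visit | At least once in three weeks |
|---|---|---|---|---|
| 9 (lowest count above 8) | 2.1 | ≥3 | 35% | 1 − 0.65³ = 73% |
| 30 | 7 | ≥9 | 27% | 61% |
| 60 | 14 | ≥18 | 17% | 43% |

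Longer windows behave better. At 9 per 30 days, the 21 days of dosing give 6.3 expected, flagged at ≥8: 30%. The 12-week follow-up of Section 4.1 gives 25.2 expected, flagged at ≥32: 11%. At 30 per 30 days, the same two windows give 12% (≥27 against 21 expected) and 1.5% (≥105 against 84). Clustering of seizures, and error in the one-month baseline, would change all of these.

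**The case against.** The case for leaving the plan alone has real substance.

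- **The seizures are moved, not discarded.** Section 11.1 ties the exemption to the secondary endpoints. A reader might infer that every seizure endpoint measures only reduction, so that a rise is invisible in the efficacy analysis. The documents do not support that: seizure frequency is an endpoint in its own right with a definition that has no direction, the percentage is signed, seizure-free days can fall, and tests are two-sided (Section 15.1).
- **Serious worsening is captured.** A reader might also infer that any drug-related rise escapes the primary safety endpoint. That is too strong. Grade 3 or higher seizures remain AEs, reach the DSMB summary and can be DLTs. Hospitalizations are analysed under Section 15.3 and withdrawals are a primary tolerability endpoint. Table 7 in Section 11.1, for events that the grading criteria do not cover, places "hospitalization or prolongation of hospitalization indicated" at Grade 3. The documents do not reproduce the CTCAE seizure grades, so how often a higher frequency would itself reach Grade 3 cannot be settled from them.
- **Reporting is not forbidden.** The general AE definition could be read to cover aggravated epilepsy, the DSMB is to review all participants, and the diary is reviewed at visits.

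These points limit the concern without removing it. The endpoints that show a rise are not required before escalation. The general AE definition sits beside a specific exemption that points the other way, so the same worsening could be recorded or not. The DSMB's remit permits seizure data but does not call for them.

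**Conclusion.** The concern holds for a rise that stays within Grade 1-2. Such a rise can be of any size and contribute nothing to the AE incidence, the DLT count or the DSMB's named inputs. It is visible only in the diary, briefly in the Investigator Opinion, and in efficacy summaries where the median and response rate can mask it. It does not extend to seizures of Grade 3 or higher, or to worsening that leads to hospitalization or withdrawal.

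The conclusion rests on the wording of Sections 5, 8.5, 11.1, 14 and 15.5, not on any assumed rate. The pass probabilities and the nine-participant example are illustrations. How likely such a rise is with ABI-009 cannot be judged from the documents. The plan should be changed because the data already exist and the gap lies only in where they are sent.

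**What to change.** 1. **Section 14.** Before each escalation and before MTD expansion, give the DSMB a listing of each participant's baseline and post-dose diary seizure frequency, with signed change, and any *worse* Investigator Opinions.
2. **Sections 15.3 and 15.5, and the SAP that Section 15.1 says will follow.** Tabulate signed change by dose level. Next to the response rate, show the proportion whose frequency rose from the baseline month by a prespecified margin. Compute this over the whole dosing period and the whole follow-up period, not between weekly visits.
3. **Section 9.1.12.** Anchor the Investigator Opinion to the baseline month.

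An automatic AE for a 25% rise since the last visit is not recommended. By the calculation above it would flag about 73% of participants at the lowest qualifying frequency within three weeks by chance alone, and so contaminate the primary endpoint.

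**Cost.** One listing, one table and short wording changes. The diary is already submitted daily through REDCap (Section 16.1). Some chance fluctuation will still appear as worsening, particularly over the three-week dosing period in participants with few seizures. The table should therefore be read as description and not as a test.
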